**NCT03790280**

### **Statistical Analysis Plan (SAP):**

Our primary comparisons will be the comparison of post-surgery seizure free-time between the SOC and SOC+HFO study arms. The primary analysis will be a log-rank test. The secondary analysis of the primary endpoint will be a Cox-proportional hazards regression with seizure-free survival time as the outcome. Covariates will be treatment, and subject-level characteristics (ex. age and gender). Secondary outcomes of 2-year seizure-free rate will be assessed with logistic regression models using a similar set of covariates that will be included in the Cox model. Surgical complication rates will be compared using Fisher's exact tests for the overall analysis. The intent-to-treat principal will be utilized and subjects will be included in the randomized study arms for analysis rather than the actual treatment received. We will conduct a secondary analysis based on treatment received.

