Epilepsy occurs in 0.5-0.7% of the population, of which 25% are children. About 30% of subjects with focal epilepsy do not respond well to medication, and half of them are eligible for epilepsy surgery. In recent years, the importance of early epilepsy surgery has been stressed, as successful surgery may lead to seizure- and medication-freedom and improved social and cognitive development, especially in children. The current rate of seizure freedom following epilepsy surgery is around 65%. During surgery, in most medical centers, either intra-operative ECoG is recorded to identify the irritative zone, defined by the spatial distribution of interictal spikes, or extra-operative ECoG is recorded to identify the seizure onset zone. The presence of epileptiform brain activity/spikes, or the seizure onset zone, identified by clinical neurophysiologists, is used to guide the neurosurgeon with respect to the boundaries of brain tissue that is necessary for resection to achieve seizure freedom. Spikes are considered biomarkers of the presence of epilepsy, and seizure onset zone indicates where the seizures may be generated. Neither spikes nor seizure onset zones accurately identify the location and the extent of the epileptogenic zone, defined as the cortical tissue whose complete removal is necessary to achieve post-operative seizure freedom.

High frequency oscillations (HFOs, 80-500 Hz) on ECoG have recently been identified as a new biomarker for epileptogenic tissue. Retrospective observational research, as well as more recent prospective observational studies, show that HFO presence strongly relates to, and may predict more accurately, the epileptogenic zone, and that the resection of brain tissue containing HFO may be superior than resection of brain tissue containing spikes and seizure onset zone in rendering patients seizure-free. The area showing HFOs usually overlaps with, but may be smaller than, the area with spikes

and seizure onset, and HFOs do not tend to propagate to distant sites as spikes and seizures do.

Standard Clinical Practice

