During surgery, current clinical practice is to measure epileptic activity that we call epileptic spikes (on intra-operative ECoG) or seizure onset zone (extra-operative ECoG) with EEG recordings. Current clinical standard of practice in either intra-operative ECoG or extra-operative ECoG is recorded to identify epileptic zone and seizure onset zone. The presence of epileptiform brain activity/spikes, or the seizure onset zone, identified by clinical neurophysiologists, is used to guide the neurosurgeon with respect to the boundaries of brain tissue that is necessary for resection to achieve seizure freedom. The particular part of the brain that has either of these abnormalities, is removed. We have used this method for over 40 years.

New Research HFO Method

Recently, it has been discovered that we can also measure other epileptic activity, High Frequency Oscillations or HFOs, by recording EEGs at a higher frequency rate. These HFOs on the EEG recordings appear to point out the epileptic brain tissue better than epileptic spikes or seizure onset zone.

In this study we will compare the two groups of patients to see what works best: standard clinical practice only, or standard clinical practice along with HFOs. The results of this study may change the way we operate on epilepsy surgery patients in the future.

Hypothesis: We hypothesize that the strategy of incorporating HFO data to a standard ECoG-guided resection in pediatric epilepsy surgery will result in improved postoperative seizure outcome than the traditional approach.

Objective:

The primary objective is to determine if HFO data in addition to ECoG data (experimental group, arm 1), compared to standard ECoG data alone (current standard control group, arm 2), will lead to improved post-surgical seizure outcome 1 year after surgery.

Secondary objectives include the comparison of incidence of neurologic deficits, neuropsychological outcomes (when available with clinical testing), and quality of life outcomes.

Study Design and Procedures:

A single-blinded randomized control trial including subjects with refractory focal epilepsy who undergo surgery with intra- or extra-operative electrocorticography. Surgery is

tailored by HFOs and standard ECoG interpretation (spikes on intra-operative ECoG or seizure onset on extra-operative ECoG) (arm 1), or tailored by standard ECoG alone (arm 2).

Randomization

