Informed consent will be obtained 1 to 7 days to up to 3 months prior to the day of surgery. Prior to surgery, the subject will be randomized into the cohort arm in a 1:1 ratio.

Blinding

Blinding of the clinical neurophysiologists and neurosurgeons for treatment allocation is not feasible because of the character of the intervention. Therefore, this is a single-blinded trial as subjects will be blinded to the cohort arm to minimize bias of the follow-up results. The treating neurologist, if other than the clinical neurophysiologists in this study, will remain blinded.

Number of Subjects:

30

Inclusion Criteria:

- Age 0-21
- Refractory focal epilepsy
- Planned resective epilepsy neurosurgery with ECoG, with the goal of tailoring the resection

Exclusion Criteria:

- Subjects undergoing non-resective neurosurgery

Recruitment of Subjects:

Subjects with refractory epilepsy undergoing epilepsy surgery with ECoG to guide the extent of the resection.

Length of Study Visits and detail:

This research study will not require any additional time in the hospital after surgery. However, will be following the subject for epilepsy outcome up to 12 months after surgery.

Chart review of clinical records such as neurological, MRI, EEG and other clinically relevant information pertaining to the outcome of surgery will be collected.

Subjects or their caregivers will be asked to fill out questionnaires about seizure frequency, medication and day to day function in various life areas at each visit with the neurosurgeon/neurologist.

Schedule of events below:

PRE-SURGERY	SURGERY	POST-SURGERY				
		Visit 2	Visit 3	Visit 4	Visit 5	Visit 6
0 day-3 months prior to surgery		1-7 days after surgery	3 months	6 months	9 months	12 months

Pre-Surgery

- Consent
- Neurosurgeon visit
- Baseline Questionnaire

Post-Surgery (at every visit)

- Neurosurgery/Neurology Visit
- Follow-up Questionnaires

Questionnaires will take about 30 minutes to complete. We may send the questionnaires home a week prior to a return visit to alleviate time at the doctor's office.

Questionnaires

NIH Pediatric Stroke Scale

Child Behavior Check List

Quality of Life in Epilepsy (Adults)

Quality of Life in Childhood Epilepsy

Procedure Detail:

Intra-operative ECoG, which could be pre-resection, post-resection, or both, during brain surgery would be determined based on clinical decisions. Similarly, extra-operative ECoG would also be determined based on clinical decisions, and would be pre-resection.

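### The SAP analyses a 2-year seizure-free rate, but the protocol follows seizure outcome only to 12 months

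*SAP*

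**What the plan says.** The SAP, a single paragraph, gives the secondary seizure outcome as follows: "Secondary outcomes of 2-year seizure-free rate will be assessed with logistic regression models using a similar set of covariates". For the primary endpoint it says: "Our primary comparisons will be the comparison of post-surgery seizure free-time between the SOC and SOC+HFO study arms". The test is a log-rank test, and no follow-up horizon or censoring time is stated.

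The protocol uses a different time frame:

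- **Objective.** The primary question is whether adding HFO data "will lead to improved post-surgical seizure outcome 1 year after surgery". The secondary list contains no later seizure outcome: "Secondary objectives include the comparison of incidence of neurologic deficits, neuropsychological outcomes (when available with clinical testing), and quality of life outcomes".
- **Length of Study Visits and detail.** The study "will be following the subject for epilepsy outcome up to 12 months after surgery". Post-surgery visits are at 1-7 days and at 3, 6, 9 and 12 months. Seizure reports are collected at those visits: "Subjects or their caregivers will be asked to fill out questionnaires about seizure frequency, medication and day to day function".
- **Same section, chart review.** "Chart review of clinical records such as neurological, MRI, EEG and other clinically relevant information pertaining to the outcome of surgery will be collected". No time window is given.

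**The concern.** A binary 2-year outcome needs subjects whose status at 24 months is known, and planned follow-up stops halfway there. The SAP does not say what to do with a subject whose 2-year status is unknown, so the analyst would have to choose, possibly after seeing the data. There are three obvious choices, and each answers a different question:

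- **Use only outcomes known from scheduled follow-up.** Every classified subject is then a failure, and a logistic model with one outcome class has no finite estimate.
- **Count subjects seizure-free at month 12 as successes.** The model fits, but it estimates a 12-month rate reported as a 2-year rate.
- **Fill in from whatever later chart entries exist.** Two-year status is then known only for subjects who happen to have later records, and nothing ensures that they represent the rest or are balanced between arms.

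Because the primary comparison has no stated horizon either, the SAP does not settle whether seizure-free time is to be followed for 12 months or 24.

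**Working it through.** **Time frames**

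| Item | Source | Value |
|---|---|---|
| Secondary seizure outcome | SAP | 24 months |
| Primary objective | Protocol, Objective | 12 months |
| Last scheduled outcome assessment | Protocol, schedule of events | 12 months |
| Scheduled visits after month 12 | Protocol, schedule of events | 0 of 5 |

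The gap is 24 − 12 = 12 months, so planned follow-up covers 12/24 = 50% of the window. This comparison needs no assumption.

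**Who can be classified**

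The protocol gives N = 30, randomized 1:1, taken here as 15 per arm. Let p be the proportion continuously seizure-free from surgery to month 12. The protocol's Background gives a seizure-freedom rate of around 65% without a time point, so p is assumed to lie between 0.50 and 0.80. Dropout is ignored; dropout while seizure-free would add to the undetermined group.

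If the outcome means continuous freedom since surgery:

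- undetermined at 2 years = 30p
- known failures = 30(1 − p)
- known successes = 0

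| p | Undetermined | Known failures | Known successes |
|---|---|---|---|
| 0.50 | 15 | 15 | 0 |
| 0.65 | 19.5 | 10.5 | 0 |
| 0.80 | 24 | 6 | 0 |

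If the outcome means status at 24 months whatever happened earlier, all 30 are undetermined for any p.

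With no successes, the logistic likelihood keeps rising as the intercept falls, so there is no maximum. A trial fit to 10 failures (5 per arm) and no successes behaved this way: the intercept was near −30 and still falling.

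**Error if the 12-month rate is labelled as 2-year**

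Let r be the proportion of those seizure-free at month 12 who relapse in year 2 (assumed 5% to 20%). The true 2-year rate is p(1 − r), so the overstatement is p − p(1 − r) = p × r, in percentage points:

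| | p = 0.50 | p = 0.65 | p = 0.80 |
|---|---|---|---|
| r = 0.05 | 2.5 | 3.25 | 4.0 |
| r = 0.10 | 5.0 | 6.5 | 8.0 |
| r = 0.20 | 10 | 13 | 16 |

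For the comparison of arms, suppose r is the same in both and the 12-month difference is d. The 24-month difference is then (1 − r)d, which is 95% to 80% of the 12-month one. If r differs between arms, the error can go either way.

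**Precision of a 12-month comparison**

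With 15 per arm and equal rates p, the Wald 95% half-width for the unadjusted difference is 1.96 × √(2p(1 − p)/15). The Newcombe interval combines the two Wilson intervals.

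| p | Wald (points) | Newcombe (points) |
|---|---|---|
| 0.50 | 35.8 | 31.9 |
| 0.65 | 34.1 | 31.1 |
| 0.80 | 28.6 | 28.3 |

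**The case against.** The outcome is secondary, and the primary log-rank test and the Cox model censor subjects who are seizure-free at last contact. Neither needs 24-month data, and a log-rank test does not require a fixed horizon. That stands: the primary comparison survives, and stating its horizon is a related improvement on which the finding does not depend.

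The undated chart review could supply later seizure data, so the one-class case may never arise. Later records may well exist. But a review with no window, in a protocol that limits outcome follow-up to 12 months, is not a plan to ascertain 24-month status.

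The percentage-point figures rest on assumed values of p and r, and they describe a single rate where the model compares arms. That is fair. They are illustrations; what the documents themselves establish is 12 months of follow-up against a 24-month outcome, with no assessment in the second year.

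The documents do not show which horizon was intended. The protocol is dated 26 Oct 2017, the SAP text reviewed carries no date, and part of the SAP file was not in that text. So the 12-month route is offered because it matches the protocol's objective and schedule, and the choice remains the sponsor's. No unseen text is needed to establish the conflict, since both time frames are stated explicitly.

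**Conclusion.** The concern holds with high confidence. The SAP's 2-year outcome cannot be obtained from the protocol's scheduled follow-up, and the supplied text neither provides for 24-month ascertainment nor says how unknown status is handled. This is a conflict between the two documents, not merely missing detail. Under the assumed 12-month rates, half to four-fifths of the 30 subjects would have undetermined 2-year status if the outcome means continuous freedom, and all of them if it means status at 24 months. It should be fixed, but it does not invalidate the primary analysis.

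**What to change.** In the SAP, change the 2-year seizure-free rate to a 12-month seizure-free rate and keep the planned logistic model. This agrees with the protocol's 1-year objective and visit schedule. State 12 months as the follow-up horizon of the primary seizure-free-time analysis as well.

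This changes SAP wording only and needs no extra visits or subjects. Its costs are:

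- The 2-year claim is given up, and seizure data found after month 12 fall outside the primary analysis horizon.
- The 1-year outcome that the protocol makes its primary objective is reported as a rate in a secondary analysis, beside the log-rank test.
- The estimate is imprecise: about ±28 to ±32 points (Newcombe) or ±29 to ±36 points (Wald) for the unadjusted arm difference.
- The adjusted model is thin. With treatment, age and gender, 6 to 15 subjects not seizure-free give 6/3 = 2 to 15/3 = 5 per coefficient.

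If the sponsor did intend 2 years, the protocol must specify 24-month outcome collection (source and time window), and the SAP must say how unknown 2-year status is handled and give the same horizon for the primary analysis. That takes a protocol amendment and 12 more months of outcome collection per subject.

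### Cheap improvement, secondary outcome only: the one fixed-time seizure-free rate is analysed by logistic regression, which cannot use partial follow-up; a 12-month Kaplan-Meier estimate could

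*SAP*

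**What the plan says.** The SAP compares seizure-free time after surgery between the arms. "The primary analysis will be a log-rank test", and the secondary analysis of the same endpoint is a "Cox-proportional hazards regression with seizure-free survival time as the outcome". Both methods use partial follow-up. For the rate the SAP changes method: "Secondary outcomes of 2-year seizure-free rate will be assessed with logistic regression models", with covariates like those of the Cox model (treatment, with age and gender as examples). No other seizure-free rate at a fixed time is analysed.

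Under intention to treat, "subjects will be included in the randomized study arms for analysis rather than the actual treatment received". That settles which arm a subject counts in, not what outcome value a subject with incomplete follow-up receives. The SAP gives no rule for such subjects and does not define seizure-free for the rate.

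In the Protocol, Length of Study Visits and detail says that the study "will be following the subject for epilepsy outcome up to 12 months after surgery", and the last scheduled visit is at 12 months. The same section provides for questionnaires on seizure frequency at each visit and for chart review. The Objective section asks whether adding HFO data "will lead to improved post-surgical seizure outcome 1 year after surgery". Thirty subjects are randomized 1:1.

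**The concern.** Logistic regression needs every subject's status at the horizon. Take seizure-free to mean no seizure since surgery, the reading that the SAP's time-to-event outcome suggests. A subject who relapses in month 2 and then leaves is a known failure. A subject who is seizure-free at month 8 and then leaves has no known status. Whether the outcome is known then depends on the outcome itself.

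Dropping subjects of unknown status keeps failures and loses successes. Counting them as seizure-free errs the other way. At stake are the seizure-free rate in each arm, which readers are likely to set beside the Protocol's benchmark, and some precision in a trial of 30. This holds at any horizon, including 12 months.

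**Working it through.** The plan offers no figure to reproduce here: the 30 subjects come with no dropout allowance, effect size or power.

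**Inputs.** From the Protocol: 30 subjects, 1:1, so about 15 per arm; a seizure-free rate of around 65% (Background and Rationale), given without a time point and taken here as the true rate S at the horizon. Assumed: dropout d of 10% to 30% by the horizon, independent of relapse and uniform over follow-up; relapses weighted early, at time = horizon × U², with U uniform on 0 to 1.

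**Rate within an arm.** The proportion known to be seizure-free is R = S(1 − d). A relapse goes unseen if the subject leaves first. For a subject who would relapse this has probability d × E[U²] = d/3, so observed relapses are F = (1 − S)(1 − d/3).

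| d | R | F | Leavers dropped, R/(R+F) | Leavers counted free, 1 − F | Known outcomes, 30(R+F) |
|---|---|---|---|---|---|
| 10% | 0.585 | 0.338 | 63.4% (−1.6) | 66.2% (+1.2) | 27.7 |
| 20% | 0.520 | 0.327 | 61.4% (−3.6) | 67.3% (+2.3) | 25.4 |
| 30% | 0.455 | 0.315 | 59.1% (−5.9) | 68.5% (+3.5) | 23.1 |

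Errors in brackets are in percentage points against 65%.

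**Check with another relapse model.** With exponential relapse and dropout, the rate with leavers dropped is 63.7%, 62.2% and 60.4%. In 8,000 simulated arms of 15 per setting, Kaplan-Meier averaged 0.649, 0.649 and 0.651.

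**Comparison of arms, unequal dropout.** Take no true effect, 10% dropout in one arm and 30% in the other.
- Leavers dropped: 63.4 − 59.1 = +4.3 points in favour of the better-followed arm (+3.3 under the exponential model).
- Leavers counted as seizure-free: 66.2 − 68.5 = −2.3 points.

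With a true 20-point effect (85% vs 65%) and the lower dropout in the 85% arm, dropping leavers gives 0.765/(0.765 + 0.145) = 84.1%, and 84.1 − 59.1 = 25.0 points.

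**Comparison of arms, equal dropout and timing.** With leavers dropped, the odds are R/F = S/(1 − S) × (1 − d)/(1 − d/3). The last factor is the same in both arms and cancels, so the odds ratio is not biased. Precision still falls. In simulated trials of 15 vs 15, the root-mean-square error of the difference was 0.1950 against 0.1831 for Kaplan-Meier at 20% dropout, and 0.2063 against 0.1880 at 30%. The mean squared error ratios are (0.1950/0.1831)² = 1.13 and (0.2063/0.1880)² = 1.20.

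**The horizon as written.** If follow-up ends at 12 months, nobody can be observed seizure-free at 2 years, so R = 0. The only known outcomes are failures, the rate with leavers dropped is 0/(0 + F) = 0% in both arms, and the logistic model cannot be fitted.

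**The case against.** The strongest reply is that the SAP names a model and is silent on missing outcomes; it does not plan a complete-case analysis. A reader might infer that the reported rate will be biased downward in both arms. The documents do not support that: the direction depends on a rule that is not given.

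A reader might also infer that chance imbalance in dropout between arms of 15 biases the comparison. It does not. Chance imbalance adds noise; bias needs a systematic difference in dropout or relapse timing, and the documents give no reason to expect one.

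Other parts of the reply also stand:
- The mechanism depends on an undefined endpoint. If the rate means status at the time point, an early relapse does not settle it, and Kaplan-Meier would estimate something else.
- Chart review may recover the status of some subjects who miss visits.
- The effect is modest. A false difference of 4.3 points is under a quarter of the 18-to-21-point root-mean-square error above, and one subject in 15 is 6.7 points.
- Pseudo-observation and weighted regression rely on large-sample standard errors, with about 30 × 0.35 = 10.5 relapses expected.

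These limit the size of the point but do not remove it. The named method cannot use partial follow-up that the SAP's own primary analysis uses, and silence on leavers leaves a choice between options that err in opposite directions.

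**Conclusion.** The point holds as a cheap improvement to a secondary outcome. It rests on seizure-free meaning no seizure since surgery. Under that reading, with a true rate of 65% and an assumed dropout of 10% to 30%, the rate in each arm is too low by about 1.5 to 6 points if leavers are dropped, and too high by about 1 to 3.5 points if they are counted as seizure-free. The comparison is biased only under a systematic difference between arms, by about 4 points for an assumed 10% vs 30% dropout with no true effect. With equal dropout and timing only precision is lost. Every dropout figure here is an assumption.

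The gap is most acute as written, because the 2-year horizon lies beyond the documented 12-month follow-up. A reader might infer that the primary comparison is compromised too. It is not: the log-rank and Cox analyses already use partial follow-up. Nor can a change of method alone rescue the 2-year rate, since a Kaplan-Meier estimate at 24 months has no support from 12 months of follow-up.

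**What to change.** 1. Reconcile the 2-year rate in the SAP with the Protocol's 12-month follow-up and 1-year objective, and define seizure-free for the rate as no seizure since surgery.
2. In the SAP, replace the sentence on logistic regression with wording such as: the 12-month seizure-free probability will be estimated by Kaplan-Meier in each randomized arm, and the difference reported with a 95% confidence interval.
3. For the adjusted version, regress Kaplan-Meier pseudo-observations at 12 months on arm and a small set of covariates, or use logistic regression weighted by the inverse probability of censoring. Keep covariates few, given about 10 expected relapses.

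The cost at 12 months is a few sentences and slightly more analysis, with no new data, visits or subjects. If nobody is lost, the pseudo-observations equal the plain yes/no outcomes. The downsides are the independent-censoring assumption, which the log-rank and Cox analyses already make, and large-sample standard errors with few relapses. Keeping a 2-year rate would also require follow-up beyond 12 months, which is not cheap.

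### The SAP analyses none of the protocol's three secondary objectives, names a 2-year outcome beyond the scheduled follow-up, and leaves surgical complication undefined

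*SAP*

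**What the plan says.** **Protocol, Objective.** The primary objective is seizure outcome at 1 year. On the rest: "Secondary objectives include the comparison of incidence of neurologic deficits, neuropsychological outcomes (when available with clinical testing), and quality of life outcomes".

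**Protocol, Length of Study Visits and detail.** The study "will be following the subject for epilepsy outcome up to 12 months after surgery". Charts will also be reviewed, with no end date given. The schedule has five post-surgery visits: 1-7 days, then 3, 6, 9 and 12 months. It lists a "Baseline Questionnaire" before surgery and "Follow-up Questionnaires" at every visit after it, without saying which scales each one contains. The four instruments are the "NIH Pediatric Stroke Scale", a child behaviour checklist, and an adult and a childhood quality-of-life scale. The introduction to them is "Subjects or their caregivers will be asked to fill out questionnaires".

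**Protocol, Potential Risks.** Loss of function is item 2. Surgical complication is item 3, illustrated by infection, hydrocephalus and stroke. Unexpected neurologic deficit is then named as the additional risk of the HFO method.

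**SAP.** The primary analysis is a log-rank test of seizure-free time, with a Cox model as its secondary analysis. Then: "Secondary outcomes of 2-year seizure-free rate will be assessed with logistic regression models". On safety: "Surgical complication rates will be compared using" Fisher's exact tests. Nothing is said about neurologic deficits, neuropsychology, quality of life or any of the four instruments.

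**The concern.** The two documents give different answers to what the secondary outcomes are. An analyst who follows the SAP would report a seizure outcome at a time for which no visit is scheduled, and would report none of the three comparisons that the protocol sets as objectives.

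The safety gap matters most. Arm 1 may resect tissue that the standard reading would have left, and the protocol itself says which extra harm could follow. Whether that harm enters the only planned safety comparison depends on an undefined term, which would be settled after the data are known unless the SAP settles it first. The same freedom applies to quality of life: with several possible visits and none chosen, a result can be picked from several.

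**Working it through.** **1. Objectives against analyses**

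| Outcome | Protocol | SAP |
|---|---|---|
| Incidence of neurologic deficits | Secondary objective | Not named; possibly within surgical complication |
| Neuropsychology, when available | Secondary objective | Not named |
| Quality of life | Secondary objective | Not named |
| 2-year seizure-free rate | Not an objective; last visit at 12 months | The only outcome called secondary |
| Surgical complication | Examples in the risk list | Fisher's exact test, no definition |

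The first three rows have no stated analysis. The fourth is an analysis with no matching objective and a time point 12 months after the last scheduled visit.

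**2. What the undefined term can move**

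Inputs: 30 subjects and 1:1 allocation (protocol), so 15 per arm.

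- One subject changes an arm's rate by 1/15 = 6.7 percentage points. A subject with a deficit and no other complication moves the risk difference by that amount, depending on whether deficits count.
- The test is much less sensitive than the estimate. With alpha 0.05 (assumed; the documents give none) and two-sided Fisher tests at 15 v 15:

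| Events, one arm v other | p |
|---|---|
| 0 v 3 | 0.224 |
| 0 v 4 | 0.100 |
| 0 v 5 | 0.042 |
| 1 v 6 | 0.080 |
| 1 v 7 | 0.035 |

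With no events in one arm, up to four in the other (4 × 6.7 = 27 points) leave p above 0.05. The definition can therefore change the estimate materially without changing the test result.

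**3. What an unfixed visit can do to a quality-of-life result**

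Assumptions: the scale is given at baseline and at all five post-surgery visits; scores are normal with equal variance and equal correlation ρ between any two occasions; there is no arm effect; two-sided t-test at 0.05.

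For the change from baseline at visit j, D_j = Y_j − Y_0:

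- Var(D_j) = 2σ²(1 − ρ)
- Cov(D_j, D_k) = σ²(ρ − ρ − ρ + 1) = σ²(1 − ρ)
- Corr(D_j, D_k) = (1 − ρ) / [2(1 − ρ)] = 0.5, whatever ρ is

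The chance of p < 0.05 at one or more of the five visits therefore does not depend on ρ. Simulation at 15 per arm gives about 18.5%, against about 5% at one fixed visit. With 8 per arm, an assumed number for an age-specific scale, it is about 19%.

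The protocol's figure of 30 subjects cannot be reproduced, because no alpha, power or effect size is stated. Nothing above depends on how it was chosen.

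**The case against.** **Surgical complication may be meant to include deficits.** It may. Stroke is one of the protocol's examples and could itself produce a deficit. A reader might infer that the SAP excludes neurologic harm, but the documents do not go that far. They leave it open, with the separate risk items pointing towards exclusion. Even the wide reading leaves quality of life and neuropsychology without an analysis.

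**The 2-year rate may be obtainable.** Chart review has no stated end date, so it cannot be said that 2-year data will not exist. What stands is that no visit is scheduled after 12 months and the protocol's seizure objective is at 1 year.

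**The 18.5% is not a property of the plan.** This is correct. The SAP proposes no five-visit testing, and the protocol does not say that every scale is given at every visit. The figure shows what an unspecified visit would permit, under stated assumptions. It counts findings in either direction.

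**Assessment of deficits may look unblinded.** A reader might infer this because neurosurgeons and neurophysiologists know the allocation. The protocol also blinds subjects, and the treating neurologist where that person is not one of the study's neurophysiologists. The rater is unstated, which is a narrower point. Nor do the documents say that the stroke scale is the measure of neurologic deficit.

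**Thirty subjects are too few for secondary tests.** This favours estimates with intervals over reliance on p-values. It does not excuse leaving out stated objectives. Sparing eloquent cortex that shows only HFOs also makes a large excess of deficits less likely, but the protocol still names the risk.

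**Conclusion.** The concern holds and should be acted on. On the available SAP text, all three protocol secondary objectives lack a stated analysis, the one outcome called secondary lies outside both the protocol's objectives and its scheduled follow-up, and the single safety comparison may omit the harm the protocol anticipates for the HFO arm.

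The textual mismatch needs no assumption. The 6.7 points per subject rests on 15 per arm. The 18.5% rests on an assumed alpha of 0.05, equal between-visit correlation and a scale given at baseline and all five visits. The documents do not support saying that deficits are certainly excluded, that a test result would reverse, or that the primary analysis is affected.

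**What to change.** In the SAP:

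1. List the protocol's three secondary objectives as secondary outcomes. Reconcile the 2-year seizure-free rate with the 1-year objective and the 12-month follow-up.
2. State which events, over what time window, count as a surgical complication, and whether neurologic deficit is included.
3. Report new or worsened neurologic deficit by arm as a separate endpoint. Use cumulative incidence from surgery to 12 months, so that early deficits that resolve are counted, and show deficits still present at 12 months alongside. Give the risk difference with an exact 95% confidence interval (method named) and Fisher's exact test. Name the instrument or record used and who scores it, using the blinded treating neurologist where one already sees the subject.
4. Analyse quality of life at one pre-stated visit (12 months is the last scheduled), as change from baseline where a baseline exists. Do this by instrument, without pooling the adult and childhood scales, and give estimates and intervals.
5. Report neuropsychology by arm with the number tested in each.

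The cost is SAP wording, plus confirming which scales are taken at baseline and at each visit, and who scores deficits. No new visit or instrument is needed. The downside is wide intervals at 15 per arm and few subjects on some age-specific scales.
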